Besides systemic therapy against the specific malignancy, treatment for brain metastases consists of whole brain and targeted radiotherapy and surgery. Supportive care consists primarily of glucocorticoids and antiepileptics. Directed systemic therapy is hampered by the blood brain barrier (BBB). Brain metastases have variable BBB protection leading to inconsistencies in responses to systemic therapy. 13 Once brain metastases are established, targeted and immunooncology therapies appear to have mixed responses. 13,15 Delivery of a drug to a brain metastasis would depend on physicochemical variables such as permeability, rate of flow to the metastases and distribution values. The first two would be expected to be increased with small molecules such as tyrosine kinase inhibitors. Micrometastases may be even more protected by the BBB.  If a drug cannot access the CNS or brain metastases, the patient may receive little benefit regardless of a systemic response. A drug which is an effective agent against brain metastases is particularly valuable. There are several features about melanoma brain metastases worth noting. A high percentage of patients develop them: up to 75% of melanoma patients will develop a brain metastasis. 17 It is not clear that brain metastases and melanoma are correlated with specific mutations, although patients with NRAS mutations may be at higher risk.  Melanoma is generally regarded as radio-resistant and brain metastases appear to respond at roughly the same rate as lesions elsewhere if combined with directed therapy such as vemurafenib.  Melanoma brain metastases have shown initial responses to molecularly targeted therapies, e.g., mutant BRAF inhibitors such as vemurafenib and dabrafenib. 20, 21, 22, 23, 24 Patients with melanoma NRAS mutations have responded to MEK1 inhibition. 18 However, initial impressive response rates have been followed by eventual relapse associated with resistance, mainly occurring due to paradoxical activation of the MAPK pathway via heterodimerization of RAF and hyperactivated downstream MEK signaling. Combination therapy with BRAF and MEK inhibitors provides improved responses compared to single-agent therapy. , ,  Interestingly, both types of agents are not be expected to cross the BBB, thus, suggesting a disrupted BBB in CNS melanoma, and other brain metastases Thus, the importance of drug penetration through the intact BBB in patients with brain metastases is uncertain. Matched analysis of brain metastases and systemic melanoma tumors suggests the PI-3K/AKT pathway is activated in brain metastases. 17

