# 3.2.2. CNS Penetration – Preclinical Study

A blood brain barrier penetration study of E6201 was conducted in FVBn mice., E6201, given its target activity, may have a role in treating brain metastases of several cancers, especially melanoma. Resistance in peripheral tumor sites may be overcome with the appropriate targeted therapy, however, for the subsequent brain metastases, targeted therapies must reach the metastatic sites that can be behind an intact BBB. Many targeted therapies have been shown to be substrates of efflux transport proteins (p-glycoprotein, mdr1, and breast cancer resistance protein, bcrp) that are expressed on the luminal surface of the BBB capillary endothelial cells. In developing a rational dosing regimen for brain metastases, it is necessary to know the rate, extent, and mechanism of BBB penetration. To date, studies using BRAF/MEK inhibitors have shown low brain penetration relative to plasma., , , 

FVBn mice were administered E6201 as a single dose, and brain-to-plasma E6201 concentration ratios were determined at different time points post-dose. The objective was to evaluate the brain distribution of E6201 in mouse models and examine the role of efflux transporters at the BBB on the CNS exposure of E6201.

Four "BBB genotype" mice were used; FVBn wild-type (control), mdr1a/b (-/-) (p-glycoprotein deficient), bcrp1 (-/-) (brcp deficient), and mdr1a/b(-/-):bcrp1(-/-) (dual knockout of both efflux proteins). LC-MS assays for both plasma and brain concentrations of E6201 were developed and used to determine the concentration-time profile (AUC) in both brain and plasma. Rapid equilibrium dialysis was used to determine unbound fractions of E6201 in brain and plasma, and a brain "partition coefficient" were determined for both total and unbound drug.

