#### 3.4.2. **Dabrafenib**

Dabrafenib will be evaluated at the approved dose and schedule for treatment of metastatic melanoma, 150 mg orally twice daily. This dose also was found to be effective and safe for treatment of metastatic melanoma in combination with trametinib in the COMBI-V and COMBI-D studies and in the BREAK-MB study of melanoma metastasized to the brain.

Therefore, to maximize the potential for activity in subjects with CNS metastases from BRAF- or MEK-mutated melanoma, under Amendment 3 of the study, E6201 will be evaluated at a dose of 320 mg/m^2 twice weekly Days 1, 4, 8, 11, 15 and 18, repeated every 28 days during the Combination Safety Run-In Phase, plus dabrafenib at a dose of 150 mg orally twice daily, with E6201 and dabrafenib dose reduction criteria for management of toxicity.

28 Confidential December 31, 2019

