## 6.2. Subject Exclusion Criteria

Subjects who meet any of the following criteria will be excluded from the study:

- Urgent need of treatment to prevent acute neurologic deterioration, including urgent neurosurgery or radiotherapy
- Symptoms of uncontrolled intracranial pressure
- Symptomatic or untreated spinal cord compression
- Prior treatment with any chemotherapeutic or investigational agent
- Prior treatment with any BRAF and/or MEK inhibitor for metastatic disease
- Prior treatment with > 1 line of immunotherapy for metastatic disease
- Serious cardiac condition within the last 6 months, such as uncontrolled arrhythmia, myocardial infarction, unstable angina or heart disease defined by the New York Heart Association (NYHA) Class III or Class IV (APPENDIX C)
- QT interval corrected for rate (QTc) > 480 msec on the ECG obtained at Screening using Fridericia method for QTc calculation
- Active infection with human immunodeficiency virus (HIV), hepatitis B virus (HBV) or hepatitis C virus (HCV) requiring systemic antiviral treatment within the last week prior to study treatment

Confidential 40
December 31, 2019 Protocol Amendment 4

• Other active infection requiring IV antibiotic usage within the last week prior to study treatment

- Any other medical intervention or other condition which, in the opinion of the Principal Investigator, could compromise adherence to study requirements or confound the interpretation of study results
- Pregnant or breast-feeding

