#### 11. STATISTICAL METHODOLOGY

#### 11.1. **Determination of Sample Size**

The statistical objective is the evaluation of the intracranial disease OR rate, defined as CR or PR, on treatment with E6201 plus dabrafenib. The sample size is based on a one-arm binomial design  $H_0 \le 0.05$  ( $\le 5\%$  response rate for historical control group) versus  $H_1 > 0.05$  (> 5% response rate for experimental group). An objective response rate (OR) of 25% or greater is deemed clinically important. A total of 3 or more responses in a sample size of 18 subjects indicates the true OR rate is  $\geq 25\%$ , with power = 80%, alpha = 0.05, and provides evidence of clinical utility to move forward.

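### Three or more responses in 18 cannot show a true rate of at least 25% or clinical utility; it is at most a preliminary activity signal for the combination

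*Combined protocol and SAP*

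**What the plan says.** Section 11.1 sets a single-arm binomial test of the intracranial objective response rate on E6201 plus dabrafenib. The null is a rate of 5% or less, described as the "response rate for historical control group", and 25% is the rate called clinically important. With 18 subjects, 3 or more responses are said to show that the true rate is at least 25%, with power 80% and alpha 0.05, and the same sentence adds that this "provides evidence of clinical utility to move forward". The Synopsis and Section 5.1 say the same. In the text supplied, none of the three places gives a source or population for the 5%.

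On the partner drug, Section 3.2.1 states: "Melanoma brain metastases have shown initial responses to molecularly targeted therapies, e.g., mutant BRAF inhibitors such as vemurafenib and dabrafenib". It goes on to say that "initial impressive response rates have been followed by eventual relapse associated with resistance", without figures. Section 3.4.2 supports the dabrafenib dose partly by its use "in the BREAK-MB study of melanoma metastasized to the brain". Section 6.2 excludes "Prior treatment with any BRAF and/or MEK inhibitor for metastatic disease".

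The study is non-randomized (Section 7.4), and the Synopsis lists no reference therapy. Section 11.3.2.1 plans two-sided 95% confidence intervals for the response proportions.

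**The concern.** The sentence draws two conclusions from a count of 3, and neither follows.

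The first is about the rate. Power of 80% at 25% is the chance of passing if the true rate is 25%. It is not evidence that the true rate is 25% once the rule has been passed.

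The second is about utility. The rule uses response only; duration of response, PFS, OS and safety do not enter it. The regimen also contains a drug that the protocol itself treats as active in this disease, given to subjects who have not had that drug class for metastatic disease. Without a dabrafenib-alone arm, a pass cannot be credited to E6201.

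At stake is how a positive result would be described at the end of the study, and the development decision that might lean on that description.

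**Working it through.** **Inputs.** From Section 11.1: n = 18, pass if X ≥ 3, null rate 5%, target rate 25%, stated alpha 0.05 and power 80%. The documents give no dabrafenib-alone intracranial response rate, so a range is assumed in step 4.

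**1. The plan's own figures.** For X ~ Binomial(18, p), P(X ≥ 3) = 1 − [(1−p)^18 + 18p(1−p)^17 + 153p²(1−p)^16].

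- At p = 0.05: 1 − (0.3972 + 0.3763 + 0.1683) = 0.058 (stated alpha 0.05).
- At p = 0.25: 1 − (0.0056 + 0.0338 + 0.0958) = 0.865 (stated power 80%).

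The stated pair is not what the exact rule delivers. N = 18 can be reached by a one-sided arcsine approximation: [(1.645 + 0.842) / (2·asin√0.25 − 2·asin√0.05)]² = (2.487 / 0.596)² ≈ 17.4, rounded up to 18, with approximate power 81.2%. The sample size is therefore explicable, but the operating characteristics of the 3/18 rule should be given exactly.

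**2. What 3/18 shows.** The estimate is 3/18 = 16.7%. The exact (Clopper-Pearson) 95% interval has as its lower limit the p solving P(X ≥ 3 | p) = 0.025, and as its upper limit the p solving P(X ≤ 3 | p) = 0.025. This gives 3.6% to 41.4%. The one-sided exact p-value against 5% is 0.058. The smallest passing result therefore does not exclude 5% at the stated alpha, and its estimate lies below 25%.

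**3. What would show at least 25%.** The exact lower 95% limit is 21.5% at 8/18 and 26.0% at 9/18. A lower limit above 25% therefore needs 9 responses, not 3.

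**4. Chance of a pass if E6201 adds nothing.** Using the formula in step 1 with assumed dabrafenib-alone rates:

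| Assumed rate | P(3 or more of 18) |
|---|---|
| 5% | 5.8% |
| 10% | 26.6% |
| 15% | 52.0% |
| 20% | 72.9% |
| 30% | 94.0% |

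The 15% row also bears on the first conclusion: a true rate well under 25% passes about half the time.

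**5. Whether the monotherapy run-in fills the gap.** Section 3.4.1 reports stable disease in two of four subjects and describes no response. Even 0/4 has an exact two-sided 95% upper limit of 1 − 0.025^(1/4) ≈ 60%, so four subjects say almost nothing about E6201's own response rate.

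**The case against.** The best defence is that the hypothesis, the primary endpoint and the decision sentence all name the combination. No objective in Section 4 is to isolate E6201's contribution, and a single-arm screen is ordinary at this stage. On that reading, the disputed phrase is only a go signal for the regimen. Most of this stands: the test is a legitimate question about the combination, and the protocol nowhere states that a pass proves an E6201 effect. It does not rescue the claim of a true rate of at least 25%, nor the description of a response count as clinical utility.

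A reader might go further in four ways that the documents do not support.

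- **That dabrafenib alone would be likely to pass the rule.** The documents give no rate, and some of their text points to a low one. Section 3.2.1 says that "targeted and immunooncology therapies appear to have mixed responses", and Section 3.2.2 that "studies using BRAF/MEK inhibitors have shown low brain penetration relative to plasma". Section 6.1 admits symptomatic CNS disease, ECOG 2, and adjuvant BRAF/MEK inhibitors ended at least 12 months earlier. The rate is open, and the table in the working is conditional.
- **That the 5% null is wrong.** It is unsourced, which by itself is only a missing detail. Replacing it with a dabrafenib benchmark is not proposed. Requiring the lower 95% limit to exceed even 10% would need 6/18, which a true rate of 25% reaches with probability 28%, against 86.5% for 3/18.
- **That a pass at least demonstrates activity of the combination.** At exactly 3/18 the 5% null is not rejected at 0.05, so only a preliminary signal can be claimed.
- **That subjects or the conduct of the trial are affected.** Expansion follows from the MTD and safety review (Section 5.1), not from the response count.

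**Conclusion.** The stated conclusion does not follow from the rule. At its threshold the result is compatible with rates from 3.6% to 41.4%, fails narrowly to exclude 5%, and falls six responses short of a lower limit above 25%. Those figures are exact and rest only on the plan's own n and cut-off.

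That a pass could occur with E6201 adding nothing follows from the design and from the protocol's account of dabrafenib. How often it would occur depends on an assumed rate and runs from 6% to 94% over the range shown.

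Severity is minor. The harm is confined to the final claim and what is built on it, and the planned confidence interval would already let a careful reader see the uncertainty.

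**What to change.** In the Synopsis, Section 5.1 and Section 11.1, replace both the statement that the true rate is at least 25% and the clinical-utility clause with:

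> Three or more responses in 18 will be taken as a preliminary signal of intracranial activity of the combination that supports considering further study; it does not establish a true rate of 25% or more and is not evidence that E6201 contributes to the response.

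Beside it, give the exact operating characteristics of the rule: one-sided alpha 0.058 at 5%, and power 86.5% at 25%. In the same edit, state the source and population of the 5%.

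This keeps a stated use for the threshold. It changes wording in three places and leaves N, the 3/18 cut-off, the procedures and the planned interval untouched. The cost is a less favourable claim if the rule is met, and an openly stated alpha slightly above 0.05.

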#### 11.2. **Analysis Populations**

The full analysis set (FAS) includes all subjects who are administered any fraction of a dose of either E6201 or dabrafenib study medication. For a particular measure, the per-protocol set (PPS) includes those subjects in the FAS who have a valid baseline and one or more post-treatment assessments for that measure of interest.

The PD population consists of all subjects in the FAS who complete a baseline and at least one follow-up PD assessment.

Efficacy analyses will be conducted separately for monotherapy and combination therapy phases of the study.

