Expansion Phase: Following screening, an additional cohort of up to N=18 subjects will be treated at the E6201 plus dabrafenib combined MTD. Subjects treated at the MTD in the Combination Safety Run-in Phase will count towards accrual in the Expansion Phase. E6201 will be administered by IV infusion over a 2-hour period at the MTD and schedule determined in the Combination Safety Run-in phase, repeated every 28 days (=1 cycle), and dabrafenib will be administered orally twice daily at the MTD determined in the Combined Safety Run-in phase. Both regimens will be subject to dose reductions for toxicity, as described. Subjects who demonstrate clinical benefit (objective response or stable disease) will be allowed to continue therapy with E6201 plus dabrafenib until progression of disease, observation of unacceptable adverse events, intercurrent illness or changes in the subject's condition that prevents further study participation.

During the study, a Safety Review Committee (SRC), consisting of the actively recruiting investigators, the Sponsor Medical Monitor and study staff will review data from the Monotherapy and Combination Safety Run-in Phases before beginning the Expansion Phase, and will review data from the Expansion Phase on an ongoing basis.

The statistical objective is the evaluation of the intracranial disease objective response (OR) rate, defined as complete response (CR) or partial response (PR), on treatment with E6201 plus dabrafenib. The sample size is based on a one-arm binomial design  $H_0 \le 0.05$  ( $\le 5\%$  response rate for historical control group) versus  $H_1 > 0.05$  (> 5% response rate for experimental group). An objective response (OR) rate of 25% or greater is deemed clinically important. A total of 3 or more

Confidential 31
December 31, 2019 Protocol Amendment 4

responses in a sample size of 18 subjects indicates the true OR rate is  $\geq$  25%, with power of = 80%, alpha = 0.05, and provides evidence of clinical utility to move forward.

CNS disease response will be assessed according to 2 methodologies: Response Evaluation Criteria in Solid Tumors (RECIST v. 1.1). and Response Assessment in Neuro-Oncology – Brain Metastases (RANO-BM). Clinical benefit is defined as best response of CR), (PR) or stable disease (SD).

Non-CNS systemic disease will be assessed according to RECIST v. 1.1.

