#### 11.3.1. **Safety Analysis**

#### 11.3.1.1. Adverse Events

All safety endpoints will be summarized using descriptive statistics and will be based on the FAS dataset.

All AEs will be coded based on the Medical Dictionary for Regulatory Affairs (MedDRA; Version 17.0 or higher). An AE will be considered a treatment emergent adverse event (TEAE) if the onset is after the first dose of study drug or if the condition was present at baseline but worsened after the first dose.

All AEs for each subject will be listed, including intensity grading, relationship to study drug, action taken and outcome. Subject listings of deaths, SAEs, and AEs leading to treatment discontinuation will be provided. Subject narratives will be provided for deaths, SAEs and other significant AEs. Summary tables will be prepared to examine TEAE severity and relationship to study treatment.

Confidential 57 December 31, 2019 Protocol Amendment 4

AE summaries will be produced separately for each dose cohort and overall, each disease cohort by dose and overall, and by monotherapy combination phases of the study. All summaries will show, by subject group, dose cohort and overall, the number and percentage of subjects experiencing at least 1 TEAE of each preferred term, arranged by system organ class, and the number of occurrences of the event. Separate summaries will be produced by relationship to study medication, by severity, and for those events with an incidence rate of at least 2% in any group or overall.

SAEs will be summarized in a similar manner; overall, by relationship to study medication, and by severity.

In addition to the above, summaries of the number and percentage of subjects discontinuing the study due to AEs and, due to death, will be presented.

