#### 11.3.2. Efficacy Analysis

#### 11.3.2.1. Primary Efficacy Endpoint

The primary efficacy endpoint is the proportion of subjects with intracranial OR following E6201 plus dabrafenib treatment. Intracranial response rates will be summarized using number and percentage of subjects with a best response of CR, PR, SD or PD assessed by RECIST v. 1.1 and RANO-BM, along with 2-sided, 95% confidence intervals for the proportions.

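### If the combination run-in de-escalates, the primary response rate as written pools subjects started at a rejected dose level with those at the combined MTD

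*Combined protocol and SAP*

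**What the plan says.** Section 11.2 separates efficacy by phase only: "Efficacy analyses will be conducted separately for monotherapy and combination therapy phases of the study". The Synopsis (Statistical Methods) says the same for all efficacy endpoints. Section 11.3.2.1 defines the endpoint without reference to dose level: "The primary efficacy endpoint is the proportion of subjects with intracranial OR following E6201 plus dabrafenib treatment", summarised with a two-sided 95% confidence interval. Section 10.4.1.1 gives the same endpoint. Neither analysis set in 11.2 depends on dose level. The full analysis set takes anyone given any part of a dose, and the per-protocol set adds only a valid baseline and a later assessment.

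Section 5.1 lists six combination dose levels, plans 6 to 12 run-in subjects and requires 6 at the combined MTD before expansion. On the cohort of up to 18 it says: "Subjects treated at the MTD in the Combination Safety Run-in Phase will count towards accrual in the Expansion Phase".

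Section 11.1 gives the decision rule: "A total of 3 or more responses in a sample size of 18 subjects indicates the true OR rate is" at least 25%, "with power = 80%, alpha = 0.05, and provides evidence of clinical utility to move forward".

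Safety is handled differently. Section 11.3.1.1 says: "AE summaries will be produced separately for each dose cohort and overall".

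**The concern.** The decision to move forward concerns the regimen at the combined MTD. The efficacy text does not confine the primary rate to that regimen. After a de-escalation, subjects who started at a level closed for toxicity belong to the combination phases and received both drugs, so on the wording they enter the primary rate and its interval. The resulting figure would be an average over two or more dose pairs, at least one of which would not be taken forward.

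The plan also leaves two defensible primary sets: MTD subjects only, or all combination subjects. In an open-label single-arm trial, that choice should be fixed before responses are known. Safety tables are split by dose cohort, so the omission for efficacy looks like a drafting gap and is easy to close.

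**Working it through.** **Inputs.** From 11.1: null rate 5% (the "response rate for historical control group"), target 25% ("An objective response rate (OR) of 25% or greater is deemed clinically important"), success at 3 or more responses in 18, stated alpha 0.05 and power 80%. From 5.1: run-in of 6 to 12 with 6 at the MTD, which leaves 0 to 12 − 6 = 6 subjects at rejected levels.

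**Formula.** P(X ≥ 3 | n, p) = 1 − (1−p)^n − n·p·(1−p)^(n−1) − [n(n−1)/2]·p²·(1−p)^(n−2).

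**The plan's own figure, n = 18.** At p = 0.05: 1 − 0.3972 − 0.3763 − 0.1683 = 0.058. At p = 0.25 the same formula gives 0.865. The stated 0.05 and 80% are therefore not reproduced exactly for this rule. The sample size is: a one-sided 0.05 test with 80% power gives 17.7 by the continuity-corrected normal approximation and 17.4 by the arcsine method, both rounding up to 18. The exact baseline for what follows is 0.0581.

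**Threshold of 3 carried to a pooled set (18 at the MTD plus k at rejected levels, all with a true rate of 5%).**

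| k | n | P(≥ 3 responses) | Ratio to 0.0581 |
|---|---|---|---|
| 0 | 18 | 0.0581 | 1.00 |
| 3 | 21 | 0.0849 | 1.46 |
| 6 | 24 | 0.1159 | 1.99 |

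For n = 21: 1 − 0.3406 − 0.3764 − 0.1981 = 0.0849. For n = 24: 1 − 0.2920 − 0.3688 − 0.2232 = 0.116 (0.1159 before the terms are rounded).

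**What drives the rise.** With one common 5% rate, only n and the fixed threshold matter. Requiring 4 responses in 24 gives 0.0298 at 5% and 0.885 at 25%, with the doses still pooled.

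**Effect on the estimate, which needs no decision rule.** Take 3 responders among 18 MTD subjects: 3/18 = 16.7%, exact (Clopper-Pearson) 95% limits 3.6% to 41.4%. Add 6 rejected-level subjects with no response: 3/24 = 12.5%, limits 2.7% to 32.4%. Conversely, 2/18 = 11.1% at the MTD plus 1/6 at a rejected level also gives 3/24 = 12.5%. Pooling can move the reported rate either way. The plan does not name an interval method, so the exact one is my assumption.

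**Sensitivity, by assumption only.** The documents give no response rates by dose. If 6 rejected-level subjects responded at 10%, 15% or 25% while the MTD rate was 5%, P(≥ 3 of 24) would be 0.186, 0.266 or 0.439. The conclusion does not rest on these.

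**The case against.** The strongest reply is that the intent is clear. The Synopsis, 5.1 and 11.1 all tie the threshold of 3 to 18 subjects, and the only 18-subject group described is the cohort at the combined MTD. No section applies 3 responses to 21 or 24 subjects. The planned primary analysis is a proportion with an interval, and 11.3.1.1 assigns the full analysis set to safety while no section assigns a set to the primary endpoint. All of this stands, and it limits the point.

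A reader might infer that any de-escalation doubles the false-positive rate of the 3-response rule. The documents do not support that:

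- It needs the threshold to be carried to a set for which it was not stated.
- It needs about 6 rejected-level subjects; 3 give a ratio of 1.46.
- Dividing by the nominal 0.05, which gives 1.7 to 2.3, mixes in the separate fact that the rule already has an exact 0.058 at n = 18.
- The same 0.116 would arise with no de-escalation if 18 subjects were added to 6 MTD run-in subjects, as the additive total of 28 to 34 in 5.2 implies. That is a separate inconsistency with the accrual statement in 5.1.

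Nor is every response in a subject started at a rejected level a response at that dose, because subjects with a dose-limiting toxicity may continue at the next lower level.

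The reply does not remove the gap. The 5.1 sentence governs accrual, and Section 11 does not repeat it for analysis. Neither defined analysis set restricts dose level, so whichever is used, the phase grouping decides who is in the rate and its interval. The option to continue at a lower level also makes treatment at the MTD an ambiguous criterion, which is a reason to define the set by assigned starting dose.

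**Conclusion.** The point holds in a limited form. As written, the primary response rate and its 95% interval pool dose levels whenever the combination run-in de-escalates, and the plan does not say that the primary set is the MTD cohort. Within the planned run-in this affects 0 to 6 subjects added to 18. There is no effect if Dose Level 1 is the MTD, and the documents give no probability of de-escalation.

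The error-rate figures (0.085 at n = 21 and 0.116 at n = 24, against 0.058) are doubly conditional: on de-escalation, and on applying the threshold of 3 to the pooled set. They assume 18 MTD subjects in total and a common 5% rate. They measure a fixed threshold with a larger n, not dose mixing. The lasting problem is interpretability of the primary estimate, together with a choice of set that is still open.

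How many subjects could be at a rejected level depends on the de-escalation trigger. The footnote to the dose table in 5.1 (at least 1 of 3, or at least 2 of 6) and the later text of the same section (at least 2 of 6, with the MTD defined by at most 1 of 6) need to be reconciled by the sponsor.

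**What to change.** In 11.2 and 11.3.2.1, define the primary response rate, its 95% confidence interval and the 3-of-18 rule on subjects whose assigned starting doses are the combined MTD: run-in subjects started at that level plus the expansion cohort. State that response in subjects started at any other combination level will be reported separately by dose level, as adverse events already are, and will not enter the decision count. Align the Synopsis wording.

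The cost is protocol and SAP wording only: no added subjects, visits or assessments, and no change to any dose or clinical rule. The one downside is that responses at other combination levels would no longer support the primary claim, though they would still be reported.
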